#### Part 2: phase IIa

In the part 2, phase IIa of the clinical trial, the doses of IPH2201 will be selected by the safety committee.

In case of any grade ≥3 adverse event:

- o Treatment will be temporarily suspended for 2 weeks
- Treatment will be resumed at the same dosage in case of resolution to a grade 2 or lower
- In the absence of resolution to a grade 2 or lower, the treatment suspension will be prolonged by 2 more weeks
- In the absence of resolution to a grade 2 or lower after a 4-week suspension, the patient will be taken off study
- In case of recurrence of a grade 3 related reaction after a temporary suspension, the same suspension will apply, but after resolution to a grade 2 or lower, treatment will be resumed at the lower dose level

In case of IPH2201 treatment discontinuation, the continuation of ibrutinib treatment is left to investigator's discretion.

Release date: Edition number

GED version

12 August 2016 MOD-3783

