### IPH2201 treatment withdrawal:

- o Disease progression (IWCLL 2008 criteria)
- Adverse events: a patient may be removed from the study following a severe (grade 3) or lifethreatening (grade 4) adverse event at the discretion of the treating physician
- o Withdrawal of consent by the patient
- Major protocol deviations (i.e., non-compliance with treatment procedures)
- o Investigator's decision
- Sponsor's decision if an inacceptable toxicity observed in another patient led the Safety Committee to recommend a transient or permanent discontinuation of the study

Release date: Edition number

MOD-3783

12 August 2016

GED version

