### 3.3.1 IPH2201

IPH2201 is administered as a 60-minute intravenous (IV) infusion starting on week 0, day 1 visit. No pre-medication is to be given at 1st administration to avoid masking the potential risk of infusion reactions. However, from the 2nd administration, pre-medication with acetaminophen or anti-histamines may be prescribed at the investigator's discretion if the patient experienced any Grade 1 - 3 infusion-related AE during the previous cycle.

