## 3.3.3 Retreatment Criteria

Patients may be retreated if all the following criteria are fulfilled:

- Absence of progression or clinical deterioration
- Absence of grade 4 treatment-related non-hematologic AE following the previous administration
- o Resolution of grade 3 or higher adverse event to grade 2 or lower

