### Week 2 day 1 (W2)

As for cycle 1, IPH2201 only will be administered at week 2 day 1 (W2) visit.

The following pre-dose assessments must be done prior to IPH2201 administration:

- Concomitant illness/Concomitant medication
- Safety assessments
  - o Vital signs (including weight)
  - o Physical examination, focused on symptoms and new findings (from screening visit)
  - ECOG status
  - o Adverse events
- Pre-dose Safety laboratory (H0)
  - Biochemistry: sodium, potassium, chloride, bicarbonate, calcium, magnesium, phosphate, total proteins, and albumin, urea, uric acid, creatinine, calculated creatinine clearance, ALP, total bilirubin, LDH, AST (SGOT), ALT (SGPT), gamma glutamyl transferase (GGT), amylase, lipase, glucose, C-reactive protein (CRP) and fibrinogen
  - o Hematology: RBC, WBC with differential count, platelets, hemoglobin; MCV, hematocrit
- PK assessment at H0

IPH2201 administration should be performed 14 days +/- 3 days after the previous administration.

Redosing criteria include the resolution of any grade 3 or higher adverse event to grade 2 or lower, the absence of disease progression and the absence of grade 4 treatment-related non-hematologic AE following the previous administration.

- The following post-dose assessments are required at W2 visit:
  - Biochemistry at H0+4: sodium, potassium, chloride, bicarbonate, calcium, magnesium, phosphate, total proteins, and albumin, urea, uric acid, creatinine, calculated creatinine clearance, ALP, total bilirubin, LDH, AST (SGOT), ALT (SGPT), gamma glutamyl transferase (GGT), amylase, lipase, glucose, C-reactive protein (CRP) and fibrinogen
  - Hematology at H0+4: RBC, WBC with differential count, platelets, hemoglobin; MCV, hematocrit
  - PK assessments at H0+1 (end of IPH2201 infusion) and H0+3 (2 hours after end of IPH2201 infusion)

Release date: Edition number

MOD-3783

12 August 2016

**GED** version

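### Protocol 3.3.1 resumes IPH2201 at the same dose after any resolved AE of grade 3 or higher and lacks the grade 4 exception set by the retreatment criteria in 3.3.3

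*Protocol*

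**What the plan says.** Protocol section 3.3.1 has one part for phase Ib and one for phase IIa. Both are triggered by any adverse event of grade 3 or higher, with no limit by relatedness or by type of toxicity. In phase IIa the first step is "Treatment will be temporarily suspended for 2 weeks"; in phase Ib it is one week. The next step is the same in both parts: "Treatment will be resumed at the same dosage in case of resolution to a grade 2 or lower". If the event has not resolved after the extended suspension, the patient comes off study. The last bullet lowers the dose level: "In case of recurrence of a grade 3 related reaction after a temporary suspension". Neither part mentions section 3.3.3.

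Section 3.3.3 opens with "Patients may be retreated if all the following criteria are fulfilled". It lists three criteria:

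- no progression or clinical deterioration;
- "Absence of grade 4 treatment-related non-hematologic AE following the previous administration";
- resolution of any AE of grade 3 or higher to grade 2 or lower.

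The synopsis gives the same list as the IPH2201 re-dosing criteria. The visit text gives "the absence of grade 4 treatment-related non-hematologic AE following the previous administration" as a re-dosing criterion at week 2 and week 4 in phase Ib (sections 6.2.1.2 and 6.2.1.3) and at week 2 in phase IIa (section 6.2.2.2).

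**The concern.** A trigger of grade 3 or higher includes grade 4. For a grade 4 event that is related to treatment and non-hematologic, section 3.3.1 says that dosing will restart at the same dose once the event has come down to grade 2. Section 3.3.3 says that the patient does not qualify for another dose. A grade 4 infusion reaction that settles within days is the obvious example.

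The stake is the safety of the individual patient. Followed as written, 3.3.1 re-exposes a patient to the full dose of an investigational antibody after a life-threatening related reaction. It is also a matter of uniform dosing: phase Ib runs at 4 sites and phase IIa at up to 10, and two sites with the same patient could act differently and each cite the protocol.

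**Working it through.** The plan states no figure on this point, so the check sets the rules side by side. Take a first event after the previous dose, resolved to grade 2 or lower within the allowed suspension, in a patient without progression or clinical deterioration.

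| Event | Section 3.3.1 | Section 3.3.3 |
|---|---|---|
| Grade 3, any kind | resume, same dose | retreatment allowed |
| Grade 4, unrelated | resume, same dose | retreatment allowed |
| Grade 4, related, hematologic | resume, same dose | retreatment allowed |
| Grade 4, related, non-hematologic | resume, same dose | retreatment not allowed |

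The rules differ only in the last row.

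**Could resolution satisfy the grade 4 criterion?** One might read that criterion as met once the event is no longer present. The list itself argues against this. Its third item already requires every AE of grade 3 or higher, grade 4 included, to have come down to grade 2. On that reading the grade 4 item would add nothing. It has a function only if it bars re-dosing even after resolution. Waiting does not help either: while the drug is withheld, the previous administration remains the one that the event followed.

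**Which rule is intended?** Three features of the text point to the bar.

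1. It stands in five places: section 3.3.3, the synopsis and three visit descriptions.
2. Section 3.3.1 allows premedication before later doses "if the patient experienced any Grade 1 - 3 infusion-related AE during the previous cycle". It makes no such provision after a grade 4 reaction.
3. The recurrence bullet in 3.3.1 names grade 3 reactions and gives no rule for grade 4.

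**Largest possible difference for one patient.** Section 3.4 plans 4 two-week cycles plus 11 four-week cycles in phase IIa, and 4 plus 12 in phase Ib, with one IPH2201 dose per cycle.

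- Phase IIa: 4 + 11 = 15 doses, so 15 − 1 = 14 remain after dose 1.
- Phase Ib: 4 + 12 = 16 doses, so 16 − 1 = 15 remain after dose 1.

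After a qualifying event at dose 1, a patient could receive up to 14 or 15 further doses under 3.3.1, and none under 3.3.3. This is a ceiling. It assumes that the event follows the first dose, resolves in time and does not recur, and that nobody stops treatment for another reason.

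**The case against.** The strongest reply is that 3.3.3 is a gate on every re-dose, and that 3.3.1 only sets the length of the hold and the dose on return. Section 3.3.1 also omits the progression criterion, and nobody would read it as ordering IPH2201 for a progressing patient. On this view the sections can be applied together, and only a cross-reference is missing.

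Much of this stands. A careful site can reach the stricter rule, and 3.3.1 need not be read as overriding 3.3.3. But no text gives 3.3.3 priority. The comparison with progression is also incomplete: 3.3.1 does not address progression, and section 3.5.1 separately requires treatment to stop. Grade 4 events lie within the stated trigger of 3.3.1, and its wording for them is mandatory.

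Three stronger inferences are tempting, and the documents do not support them.

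- A reader might take the withdrawal criteria (synopsis and section 4.3) as another conflicting rule, because they leave removal after a grade 3 or 4 event to the treating physician. They are a permission to withdraw and do not authorize re-dosing, so they are compatible with the bar. They also do not settle the question.
- A reader might count the dosing visits whose description omits the bar as further conflicts. The criteria in 3.3.3 and the synopsis are general and apply at every administration, and those visit descriptions do not repeat the resumption rule of 3.3.1 either.
- A reader might treat the ceiling of 14 or 15 doses as an expected effect. The documents give no rate of such events.

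The safety committee is a partial safeguard, since these events count as unacceptable reactions. But its recommendation to stop or reduce the dose is tied to two such reactions, and its routine phase IIa review is six-monthly, with ad hoc involvement for a major safety issue. The decision on the next dose for one patient rests on the written rule.

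**Conclusion.** The point holds as a conflict between two dosing rules, in both phases, limited to grade 4 treatment-related non-hematologic AEs that resolve to grade 2 or lower. For every other AE that resolves, the two sections agree. The repeated bar is evidently the intended rule, and 3.3.1 lacks the matching exception. This rests on reading the grade 4 criterion as applying after resolution, which the structure of the list supports.

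The conflict should be corrected because the wrong reading has a serious consequence for the patient and the correction is small. No number of affected patients can be given.

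A reader might infer that the efficacy conclusion is also at risk. The documents do not support that. The rule of at least 4 complete responses in 27 patients does not depend on the re-dosing rule. Under SAP section 4.2.2, stopping IPH2201 excludes a patient from the main endpoint population only if the reason is progression within 8 weeks, so stopping for a grade 4 AE does not remove a patient from the denominator.

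**What to change.** In both parts of section 3.3.1, replace the lead-in to the bullets with:

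> After a grade 4 treatment-related non-hematologic AE, IPH2201 is not given again (section 3.3.3). In case of any other grade ≥3 adverse event:

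Leave the bullets unchanged. Add the first of these two sentences to the adverse-event line of the withdrawal criteria in both the synopsis and section 4.3. Changing only one of them would create a new mismatch between synopsis and body. The bar in 3.3.3, the synopsis re-dosing criteria and the three visit descriptions stays as it is.

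If the sponsor does intend re-dosing after such an event has resolved, the criterion must instead be removed from all five places and the decision justified.

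The cost is a short amendment. Because it concerns a dosing rule, it needs IEC/IRB approval under section 12.2. Sample size, decision rule and SAP do not change.

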3.3.2 Ibrutinib

Ibrutinib will be administered according to the FDA-approved label, i.e., at the dose of 420 mg (three 140 mg capsules) orally once daily. Ibrutinib will be supplied commercially.

In the part 1, phase Ib of the clinical trial, ibrutinib will be administered starting at 3rd administration of IPH2201 at week 4, in the absence of unacceptable toxicity.

In the part 2, phase IIa of the clinical trial, both drugs will be administered on the same day, from the 1st administration and from the beginning of the phase IIa at week 0.

[figure not shown]
Adverse events (AEs): interrupt ibrutinib therapy for any grade  $\geq 3$  or greater non hematological AEs, grade  $\geq 3$  neutropenia with infection or fever or grade 4 hematological toxicities. Once the symptoms of the toxicity have resolved to grade 1 or baseline (recovery), ibrutinib may be reinitiated at the starting dose. If the toxicity reoccurs and persists or after discontinuation of IPH2201, reduce dose by one capsule (140 mg per day). A second reduction of dose by 140 mg may be considered as needed. If these toxicities persist or recur following 2 dose reductions, discontinue ibrutinib. For patients with mild liver impairment (Child-Pugh class A), the recommended dose is 140 mg daily (one capsule).

Concomitant medications: strong CYP3A inhibitors (see appendix V) are contra-indicated if they should be given more than 7 days. If a strong CYP3A inhibitor should be given 7 days or less consider interrupting ibrutinib until the CYP3A inhibitor is no longer needed.—If a moderate inhibitor (see appendix V) should be given for any time period, reduce ibrutinib dose to 140 mg. Strong CYP3A inducers (see appendix V) should be avoided with ibrutinib.

Elective procedures: stop ibrutinib 3 days before and after a minor procedure (e.g. invasive exploration such as a colonoscopy) and 7 days before and after a major procedure (e.g. surgery).

In case of ibrutinib treatment discontinuation, the continuation of IPH2201 treatment is left to investigator's discretion at the same dosage and schedule as before ibrutinib discontinuation.

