### o Ibrutinib

### Adverse events (AEs):

Interrupt ibrutinib therapy for any grade  $\geq$  3 non hematological AEs, grade  $\geq$  3 neutropenia with infection or fever or grade 4 hematological toxicities. Once the symptoms of the toxicity have resolved to grade 1 or baseline (recovery), ibrutinib may be reinitiated at the starting dose. If the toxicity reoccurs and persists or after discontinuation of IPH2201, reduce dose by one capsule (140 mg per day). A second reduction of dose by 140 mg may be considered as needed. If these toxicities persist or recur following 2 dose reductions, discontinue ibrutinib.

Concomitant medications: strong CYP3A inhibitors (see appendix V) are contra-indicated if they should be given more than 7 days. If a strong CYP3A inhibitor should be given 7 days or less consider interrupting ibrutinib until the CYP3A inhibitor is no longer needed. If a moderate inhibitor (see Appendix V) should be given for any time period, reduce ibrutinib dose to 140 mg.

Elective procedures: stop ibrutinib 3 days before and after a minor procedure (e.g. invasive exploration such as a colonoscopy) and 7 days before and after a major procedure (e.g. surgery).

In case of ibrutinib treatment discontinuation, the continuation of IPH2201 treatment is left to investigator's discretion, at the same dosage and schedule as before ibrutinib discontinuation.

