#### CONFIDENTIAL

Release date: Edition number

GED version

MOD-3783

12 August 2016

10. Abnormal cardiac status with any of the following:

- Unstable angina
- o Myocardial infarction within the last 6 months
- o Arrhythmia requiring treatment and which is not stabilized by the treatment
- QTc > 500ms (Bazett)
- o History of documented congestive heart failure (New York Heart Association functional classification III-IV)
- 11. Pregnant women are excluded from this study; breastfeeding should be discontinued
- 12. Current active infectious disease or positive serology for HIV and/or positive PCR for HCV, or chronic HBV infection (positive Hbs Aq, and in patients treated by IVIG, a positive HBV PCR)
- 13. History of another malignancy within 3 years, except a malignancy, which in the opinion of the investigator is inactive and would not limit survival to less than 5 years
- 14. History of allogeneic stem cell or solid organ transplantation
- 15. Intermittent or continuous renal replacement therapy
- 16. Concomitant treatment with other investigational agents
- 17. Systemic treatment with steroids or other immunosuppressive agents within 30 days prior to entry, but physiological replacement with hydrocortisone or equivalent is acceptable
- 18. Patients who are on chronic treatment with strong or moderate CYP3A4 inhibitors (e.g., nefazodone, aprepitant, ciprofloxacin, diltiazem, erythromycin, fluconazole, grapefruit juice, imatinib, verapamil) or inducers (e.g., carbamazepine, rifampin, phenytoin and St. John's Wort) should be excluded from study entry (see Appendix V)
- 19. Patients should not have psychological, familial, sociological, or geographical conditions that do not permit medical follow-up and compliance with study protocol

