### 5.3 CONCOMITANT TREATMENTS

### 5.3.1 Permitted

No pre-medication is to be given at 1st administration to avoid masking the potential risk of infusion reactions. However, from the 2nd administration a pre-medication by acetaminophen or anti-histamine drug might be prescribed, at the investigator discretion, if the patient experienced any grade 1 to 3 infusion-related AE at the previous cycle.

Patients should receive all necessary supportive care in the form of treatment or prophylaxis as clinically indicated e.g. transfusion of blood products, antibiotics, anti-histaminics, analgesics.

Corticosteroids by systemic route are prohibited, as mentioned below in section 5.3.2.

Any blood product and/or concomitant medication administered should be recorded in the medical record and eCRF, including dose, start and stop dates.

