## 5.3.2 Not Permitted

The following concomitant treatments are not permitted until the end of the treatment period (End of Treatment) and must be stopped before the start of treatment accordingly with their pharmacological effects:

- o Any chemotherapy or other systemic anti-tumor therapy (including other monoclonal antibody)
- Any irradiation
- o Corticosteroids IV or *per os* (PO) (except for the treatment of grade ≥ 3 infusion reaction)
- Other Investigational drugs
- o Cytokines and/or growth factors
- Immunosuppressive agents
- o Antivitamin K anticoagulants

Strong CYP3A inhibitors (see appendix V) are contra-indicated if they must be given more than 7 days. If a strong CYP3A inhibitor must be given for 7 days or less consider interrupting ibrutinib until the CYP3A inhibitor is no longer needed.-If a moderate inhibitor (see appendix V) must be given for any time period, the dose of ibrutinib should be reduced to 140 mg. Strong CYP3A inducers (see appendix V) should be avoided with ibrutinib.

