# APPENDIX V – LIST OF CYP3A4 INHIBITORS AND INDUCERS

# According to FDA Drug Development and Drug Interactions: Table of Substrates, Inhibitors and Inducers

Strong CYP3A4 inhibitors	Moderate CYP3A4 inhibitors
5-fold increase in AUC	2 but < 5-fold increase in AUC
or > 80% decrease in CL	or 50-80% decrease in CL
boceprevir,	amprenavir,
clarithromycin,	aprepitant,
conivaptan,	atazanavir,
grapefruit juice (1),	ciprofloxacin,
indinavir,	darunavir/ritonavir,
itraconazole,	diltiazem,
ketoconazole,	erythromycin,
lopinavir/ritonavir,	fluconazole,
nefazodone,	fosamprenavir,
nelfinavir,	grapefruit juice (1),
posaconazole,	imatinib,
ritonavir,	verapamil
saquinavir,	
telaprevir,	
telithromycin,	
voriconazole	

Strong Inducers 80% decrease in AUC	Moderate Inducers 50-80% decrease in AUC
carbamazepine,	bosentan,
phenytoin,	efavirenz,
rifampin,	etravirine,
St. John's wort(2)	modafinil,
	nafcillin

 The effect of grapefruit juice varies widely among brands and is concentration-, dose-, and preparation-dependent. Studies have shown that it can be classified as a "strong CYP3A inhibitor" when a certain preparation was used (e.g., high dose, double strength) or as a "moderate CYP3A inhibitor" when another preparation was used (e.g., low dose, single strength).

 The effect of St. John's wort varies widely and is preparation-dependent.

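### The moderate-CYP3A-inhibitor rule is a fixed 140 mg target, so a patient already on 140 mg ibrutinib gets no reduction

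*Protocol*

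**What the plan says.** The standard ibrutinib dose is 420 mg daily, as three 140 mg capsules. Protocol 3.3.2 sets the dose with a moderate inhibitor: "If a moderate inhibitor (see appendix V) should be given for any time period, reduce ibrutinib dose to 140 mg". The synopsis (treatment modifications, ibrutinib) repeats it: "If a moderate inhibitor (see Appendix V) should be given for any time period, reduce ibrutinib dose to 140 mg". So does 5.3.2: "If a moderate inhibitor (see appendix V) must be given for any time period, the dose of ibrutinib should be reduced to 140 mg". All three give a target dose, not a proportional cut, and none makes an exception.

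Section 3.3.2 also contains two routes to 140 mg:

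- Liver impairment: "For patients with mild liver impairment (Child-Pugh class A), the recommended dose is 140 mg daily (one capsule"). Exclusion criterion 8 removes only classes B and C, so class A patients can enrol.
- Toxicity: a first reduction of one capsule, and then "A second reduction of dose by 140 mg may be considered as needed". Ibrutinib is stopped only if toxicity persists or recurs after both steps.

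Appendix V describes a moderate inhibitor by "2 but < 5-fold increase in AUC". Interruption of ibrutinib because of an inhibitor is offered only for strong inhibitors given for 7 days or less. Exclusion criterion 18 covers use at entry: "Patients who are on chronic treatment with strong or moderate CYP3A4 inhibitors (e.g., nefazodone, aprepitant, ciprofloxacin, diltiazem, erythromycin, fluconazole" and others. For treatment on study, 5.3.1 says: "Patients should receive all necessary supportive care in the form of treatment or prophylaxis as clinically indicated e.g. transfusion of blood products, antibiotics".

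**The concern.** The rule exists to offset a rise in ibrutinib exposure. It does so by lowering the dose, yet at 140 mg there is nothing left for it to lower. A site that follows the text exactly makes no adjustment, in the patients for whom the plan has already provided a lower dose.

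The situation is foreseeable. Exclusion 18 bars chronic inhibitor use at entry, not a course begun later. Antibiotics are permitted, and Appendix V lists ciprofloxacin, erythromycin and fluconazole, as well as diltiazem and verapamil, as moderate inhibitors. Ibrutinib is planned to continue through 12 months of follow-up after IPH2201, so the period at risk is long.

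What is at stake is avoidable over-exposure in individual patients. The adverse-event rules in 3.3.2 help only once toxicity has occurred, whereas a dose rule for an interaction is meant to act before it.

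**Working it through.** **Inputs**

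- Standard dose 420 mg, capsule size and reduction step 140 mg, class A dose 140 mg, dose with a moderate inhibitor 140 mg (Protocol 3.3.2).
- AUC factor for a moderate inhibitor: 2 to <5 (Appendix V).

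**Assumptions**

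- Exposure is proportional to dose.
- The Appendix V class range applies to ibrutinib. The documents give no figure specific to ibrutinib.

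**Step 1: the dose after two reductions.** 420 − 2 × 140 = 140 mg. This equals the class A dose and the rule's target.

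**Step 2: the dose under the rule.** New dose = min(current dose, 140 mg).

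**Step 3: net exposure relative to the patient's own level before the inhibitor.** Ratio = (new dose / current dose) × AUC factor.

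| Current dose | Dose under rule | Cut | Lower end | Upper end (not reached) |
|---|---|---|---|---|
| 420 mg | 140 mg | 67% | (1/3) × 2 = 0.67 | (1/3) × 5 = 1.67 |
| 280 mg | 140 mg | 50% | (1/2) × 2 = 1.0 | (1/2) × 5 = 2.5 |
| 140 mg | 140 mg | 0% | 1 × 2 = 2.0 | 1 × 5 = 5.0 |

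From the full dose, the rule brackets the prior exposure. From 140 mg, the whole interaction remains.

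**Step 4: absolute exposure.** With the inhibitor, 140 mg corresponds to 140 × 2 = 280 up to <140 × 5 = 700 mg daily without it. This holds in every row, because everyone ends on 140 mg. A 3-fold rise gives 140 × 3 = 420 mg, the standard dose.

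**Step 5: the two groups compared.**

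- *Twice reduced for toxicity.* The absolute range of 280 to <700 mg-equivalent is the one the plan accepts for a patient cut from 420 mg. What differs is that this patient has shown lower tolerance.
- *Class A.* The protocol ties the 140 mg dose to liver impairment alone, so it leaves no allowance for an inhibitor on top. The comparison with a patient cut from 420 mg does not carry over, because that patient's 140 mg answers the inhibitor and this patient's answers the liver. The documents do not say how much class A impairment raises exposure per mg, so no equivalent dose for a normal liver can be given.

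**Step 6: is the gap closed elsewhere?** The synopsis, 3.3.2 and 5.3.2 carry the same target. The interruption option is limited to strong inhibitors, and exclusion 18 is limited to entry. No provision covers a patient already at 140 mg.

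**The case against.** The best reply is that the rule also works as a ceiling: nobody takes more than 140 mg with a moderate inhibitor, and a twice-reduced patient ends no higher than one cut from 420 mg. That stands, and it makes the point weaker for the toxicity group. It does not answer the class A case.

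Other safeguards exist. Ibrutinib is interrupted for grade 3 or higher non-hematological events, for grade 3 or higher neutropenia with infection or fever, and for grade 4 hematological toxicity. It is stopped if toxicity persists or recurs after two reductions. Nothing prevents an investigator from choosing another drug or holding ibrutinib. These provisions are real, but they are either reactive or left to discretion. The protocol also says ibrutinib follows the FDA label; what the label says on this combination cannot be checked from the documents.

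Several stronger inferences are tempting and should not be drawn:

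- *That a moderate inhibitor necessarily cancels the second toxicity reduction.* This depends on applying a class range to ibrutinib and on dose-proportionality, both of which are assumptions.
- *That frequent severe infections on ibrutinib (1.1.5.1) make the gap common.* A grade 3 or higher infection already triggers interruption. What remains is milder infection, prophylaxis, cardiac drugs, and courses that run on after ibrutinib restarts.
- *That SAP 9.2 shows such patients are expected.* It plans a count of reductions to one capsule. A planned count is not an expectation, and as worded it could include reductions made because of an inhibitor.
- *That dose finding is at risk.* Ibrutinib starts at week 4 and the DLT window closes at week 8. A class A patient would need an inhibitor and a qualifying event within those four weeks, and the safety committee reviews causality in phase Ib. The effect is possible but remote.

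**Conclusion.** The gap is real and narrow. As written, the rule makes no reduction for a patient already on 140 mg. It matters most in Child-Pugh class A and less after two toxicity reductions. On the two stated assumptions, exposure rises 2- to <5-fold over the patient's prior level, against 0.67- to <1.67-fold for a patient cut from 420 mg.

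The number affected cannot be derived from the documents and is probably small. The trial enrols at most 45 patients. Class A patients must also meet the liver-function limits of inclusion criterion 7, the second toxicity reduction is optional, and in either group the inhibitor must be started on study.

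A reader might infer that the efficacy conclusion is compromised. The documents do not support that: alpha, power and the requirement of at least 4 complete responses in 27 do not depend on this rule. This is a dosing-safety gap worth closing because closing it is cheap.

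**What to change.** Add one sentence to Protocol 3.3.2, to 5.3.2 and to the ibrutinib part of the synopsis:

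*If a moderate CYP3A inhibitor is needed in a patient already receiving 140 mg, use a non-inhibiting alternative where possible; otherwise interrupt ibrutinib for a short inhibitor course and resume at 140 mg; for a long-term need, discuss with the sponsor's medical representative before starting the inhibitor.*

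With 140 mg capsules there is no lower non-zero daily dose, so avoidance or a hold is the natural remedy. The long-term case is kept separate because drugs such as diltiazem or verapamil could otherwise mean an open-ended hold of an active agent in a trial that assesses complete response at 52 weeks.

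The cost is one sentence in three places and a temporary ibrutinib hold in the few patients concerned. Sample size, endpoints and analysis do not change.
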